### **6.2.1. Preparation and Dispensing**

Investigational Product, PF-06946860 (CC1), and diluent (depending upon the dose) will be used to prepare doses for administration. See the IP manual for instructions on how to prepare the investigational product for administration. Investigational product should be prepared and dispensed by an appropriately qualified and experienced member of the study staff (eg, physician, nurse, physician's assistant, nurse practitioner, pharmacy assistant/technician, or pharmacist) as allowed by local, state, and institutional guidance.

## **6.3. Measures to Minimize Bias: Randomization and Blinding**

### **6.3.1. Allocation to Investigational Product**

This is an open-label study; however, the specific investigational product dispensed to the participant will be assigned using an interactive response technology (IRT) system (interactive Web-based response [IWR]). The site will contact the IRT prior to the start of investigational product administration for each participant. The site personnel (study coordinator or specified designee) will be required to enter or select information including but not limited to the user's identification (ID) and password, the protocol number, and the

participant number. The site personnel will then be provided with a treatment assignment, randomization number, and dispensable unit (DU) or container number when investigational product is being supplied via the IRT system. The IRT system will provide a confirmation report containing the participant number, randomization number, and DU or container number assigned. The confirmation report must be stored in the site's files. The site will record the investigational product assignment on the applicable case report form, if required.

Investigational product will be dispensed at the clinic study visits as summarized in the [SoA](#).

The study-specific IRT reference manual and IP manual will provide the contact information and further details on the use of the IRT system.

#### **6.4. Study Intervention Compliance**

All doses of investigational product will be administered by the appropriately designated study staff at the investigator site.

#### **6.5. Concomitant Therapy**

Participants may be entering the study at the first or second cycle of their current course of standard of care anti-tumor therapy. Participants will receive standard of care anti-tumor therapy as described in the Inclusion criteria (See [Section 5.1](#)) and will receive any other supportive treatments or interventions as indicated by standard of care for their clinical condition.

Hormonal contraceptives, that meet the requirements of this study, are allowed to be used in participants who are women of childbearing potential (WOCBP) (see [Appendix 4](#)).

Concomitant treatment considered necessary for the participant's well-being may be given at discretion of the treating physician.

All concomitant treatments, blood products, as well as nondrug interventions (eg, paracentesis) received by participants from screening until the end of study visit will be recorded on the case report form (CRF) with indication, daily dose, and start and stop dates of administration. All participants will be questioned about concomitant treatment at each clinic visit.

Treatments taken within the 28 days before the first dose of IP will be documented as a prior treatment. Treatments taken after the first dose of IP will be documented as a concomitant treatment.

#### **6.6. Dose Modification**

There is no dose modification of PF-06946860 anticipated for a given participant in this study.

## **6.7. Intervention After the End of the Study**

No intervention will be provided to study participants at the end of the study.

## **7. DISCONTINUATION OF STUDY INTERVENTION AND PARTICIPANT DISCONTINUATION/WITHDRAWAL**

### **7.1. Discontinuation of Study Intervention**

In rare instances, it may be necessary for a participant to permanently discontinue investigational product. If investigational product is permanently discontinued, the participant will remain in the study for follow up. Note that discontinuation of investigational product does not represent withdrawal from the study.

If a safety or tolerability concern arises, in particular if not responsive to symptomatic management, dosing with IP may be stopped in an individual participant at investigator discretion.

Any participant who prematurely withdraws after being randomized and during active study intervention, (Day 1 through Week 12) should return for an early withdrawal visit and then enter into the follow-up period.

See [Section 1.3](#) for data to be collected at the time of intervention discontinuation and follow-up and for any further evaluations that need to be completed.

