### **1.3. Schedule of Activities (SoA)**

The SoA table provides an overview of the protocol visits and procedures. Refer to the **STUDY ASSESSMENTS AND PROCEDURES** section of the protocol for detailed information on each procedure and assessment required for compliance with the protocol.

The investigator may schedule visits (unplanned visits) in addition to those listed in the SoA table, in order to conduct evaluations or assessments required to protect the well-being of the participant.

Visit Identifier	Screening a	Treatment									EOT	Follow Up b				
Visit Number	v1	v2	v3	v4	v5	v6	v7	v8	v9	v10	v11	v12	v13	v14	v15	
Study Week (relative to Day 1)		w1	w2	w3	w4	w5	w6	w9	w12	w13	w14	w15	w18	w24		
Study Day (relative to Day 1 dosing)	-28 to -1	1	8	15	22	29	36	43	64	85	92	99	106	127	169	
Visit Window (days)		±1	±1	±3	±1	±1	±3	±3	±3	±1	±1	±1	±3	±7	±7	
Clinic Visit	X	X		X			X	X	X			X	X	X	X	
At-Home Visit c			X	X		X	X				X	X				
Informed Consent and Registration	X															
Review of Eligibility Criteria	X	X														
Medical History and Demography	X															
Record Prior or Concomitant treatments	X	X		X			X	X	X			X	X	X	X	
Monitor Serious/nonserious AEs d	X	X	→	→	X	→	→	X	X	X	→	→	X	X	X	X
Review contraception use	X	X		X			X	X	X			X	X	X	X	
Physical Examination e	X	X		X			X	X	X			X	X	X	X	
Weight (+ Height at Screening only)	X	X		X			X	X	X			X	X	X	X	
Supine vital signs f	X	X		X			X	X	X			X	X	X	X	
Supine standard 12-Lead ECG g	X	X		X			X	X	X			X	X	X	X	
CT scan	X h,i							X h,i	X h,i,j						X j	
ECOG Performance	X									X			X	X	X	X
CCI																
Randomization		X														
Administration of IP (PF-06946860, SC) l		X		X			X	X	X							
Anti-tumor therapy prescribed per SoC m		X	→	→	→	→	→	→	→	→						
Safety Labs (Blood and Urine):	X	X		X			X	X	X			X	X	X	X	
Pregnancy Test for females (Blood and/or Urine) n	X	X		X			X	X	X			X	X	X	X	
GDF-15 blood levels (Roche assay) o	X															
GDF-15 blood levels (Internal assay(s)) o,p	X	X	X	X	X	X	X	X	X	X	X	X	X	X	X	
PF-06946860 serum PK p		X	X	X	X	X	X	X	X	X	X	X	X	X	X	
Immunogenicity (ADA/NAb) p		X		X	X		X	X	X			X	X	X	X	
Prep D1 banked biospecimen q		X														
Prep B1.5 & B2 banked biospecimen q		X	X		X		X	X	X	X	X	X	X	X	X	

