- j. CT scan: To be completed at the ET visit if a CT scan has not been completed in the prior 6 weeks. However, a CT scan at the ET visit is not needed if the ET is before Week 4 or if a CT scan was performed at Week 12.

**CC** [REDACTED]

- l. **PF-06946860** dosing can be initiated at the start of the first or second cycle of the standard of care anti-tumor therapy. If the standard of care anti-tumor therapy is to be administered on the same day of dosing with PF-06946860, the IP will be the first drug administered during the clinic visit and must be given at least 0.5h prior to administration of SOC anti-tumor therapy. If SoC anti-tumor therapy is paused, adjusted or discontinued during the 12 week treatment period, this would not be considered a protocol deviation. PF-06946860 administration is to continue as prescribed by the protocol.
- m. The **SoC anti-tumor therapy** may continue beyond the study 12-week PF-06946860 treatment period according to the SOC anti-tumor therapy for each cancer type and the treating physician's clinical judgment; this would not be considered a protocol deviation.
- n. **Blood and/or Urine pregnancy** test may be performed at the discretion of the PI.
- o. Two GDF-15 samples will be collected at Screening. One sample will be tested using the Roche GDF-15 assay for determination of enrollment eligibility. Another sample will be analyzed using the internal Pfizer GDF-15 assay(s).

p. **GDF-15, PK and Immunogenicity blood samples** will be collected as described in [Section 10.19](#). On dosing days (Day 1, Weeks 3, 6, 9, and 12), these blood samples will be collected prior to PF-06946860 administration (ie, pre-dose). Additionally, on Day 1 and Week 12, **post-dose** blood samples will be collected, **one for PK and one for GDF-15** at each visit. These **post-dose** blood samples will be collected at a minimum of 3h post PF-06946860 administration or at a maximum by the end of the clinic visit.

q. **Prep D1, B1.5 and B2 banked biospecimen** samples collected during clinic visits will be collected prior to PF-06946860 administration. For Prep D1, if not collected on the designated collection day, collect at the next available time point when biospecimens are being collected in conjunction with a participant visit.

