## 4. STUDY DESIGN

### 4.1. Overall Design

This is a Phase 1b, open-label study in participants with advanced metastatic NSCLC, pancreatic cancer or colorectal cancer and cachexia, and elevated circulating GDF-15 concentrations. Baseline GDF-15 levels will be assessed at screening to determine eligibility for participation.

Following the 28-day screening period to confirm eligibility, the study will consist of a treatment period of 12 weeks and a follow-up period of 12 weeks. The total duration of participation in this study is approximately 24 weeks (not including the screening period).

During the 12-week treatment period in Cohort 1, participants will receive a total of 5 doses of PF-06946860, administered subcutaneously (SC), every 3 weeks (Q3W).

This study will consist of up to 2 cohorts. In each study cohort, approximately 8 participants will be enrolled such that approximately 6 evaluable participants complete the study. Participants who discontinue prior to completion of the study may be replaced, at the discretion of the investigator and sponsor. It is planned that the 2 cohorts will be enrolled sequentially and will follow similar schedules of activity. The optional Cohort 2 may be conducted at the discretion of the Sponsor, with data emerging from Cohort 1 informing the dose level and/or frequency to be administered in Cohort 2 (see [Section 4.3](#)).

Based on emerging data, the dose, schedule, length and number of follow-up visits required may be adjusted; in this case, details will be provided to the investigator in writing or via a protocol amendment, as appropriate, prior to initiation of the cohort.

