Therefore, it is hypothesized that cachexia in many types of cancer, including NSCLC, pancreatic cancer, and colorectal cancer, is largely mediated via GDF-15 and that suppression of GDF-15 in these patients may lead to improvement in serious aspects of cachexia such as anorexia leading to unintended weight loss, fatigue and impaired mobility. Furthermore, given the observations of GDF-15 elevation with platinum therapy, patients receiving standard of care anti-tumor treatment that includes systemic platinum-based therapy, may be a specific population that could potentially gather additional benefit from GDF-15 inhibition.

Study C3651009 represents the first administration of PF-06946860 in patients with cancer and cachexia. As such, an open-label design and a small sample size have been implemented in order to transparently establish an initial assessment of clinical safety, PK, PD and immunogenicity of this novel therapy.

A treatment duration of 12 weeks is consistent with available pre-clinical toxicology coverage and to support development of PF-06946860 in subsequent Phase 2 studies. A treatment duration of 12 weeks should provide sufficient safety information to inform subsequent PF-06946860 Phase 2 studies. After the 12-week treatment period, participants will be followed up for 12 weeks post last dose. Based on the preliminary population PK/PD simulation results, it is anticipated that at 12 weeks post last dose of **CCI** PF-06946860 the unbound PF-06946860 concentrations will be below the level that would be expected to fully suppress GDF-15.

PF-06946860 will be dosed via subcutaneous injections, every 3 weeks. However, the dosing frequency in Cohort 2 may be adjusted based upon emerging data from Cohort 1.

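### The protocol gives no single visit set or time anchor for participants who stop PF-06946860 before Week 12, and the SAP would then count samples taken 42 to 105 days after the last dose as Week 15 troughs

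*Protocol*

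**What the plan says.** Four parts of the plan bear on this.

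- **Protocol Section 1.3 (SoA).** All visits, follow-up included, run on one clock: "Study Week (relative to Day 1" and "Study Day (relative to Day 1 dosing" head the timing rows. Doses fall on Days 1, 22, 43, 64 and 85. The visits after Week 12 fall on Days 92, 99, 106, 127 and 169 (Weeks 13, 14, 15, 18 and 24).
- **Protocol Sections 4.1 and 4.2.** Section 4.1 says "the study will consist of a treatment period of 12 weeks and a follow-up period of 12 weeks". Section 4.2 counts the second part from dosing: "After the 12-week treatment period, participants will be followed up for 12 weeks post last dose". It justifies that length by the drug concentration expected at that time.
- **Protocol Section 7.1.** On stopping the drug: "If investigational product is permanently discontinued, the participant will remain in the study for follow up". On premature withdrawal between Day 1 and Week 12: the participant "should return for an early withdrawal visit and then enter into the follow-up period". The section then points to Section 1.3 "for data to be collected at the time of intervention discontinuation and follow-up and for any further evaluations that need to be completed".
- **SAP Sections 3.2, 3.3.2, 4, 6.2 and 6.3.2.** Trough time points are the pre-dose samples at Weeks 3, 6, 9 and 12 and the Week 15 sample. PK and GDF-15 summaries are by nominal time point. A participant enters the PK or PD population with one dose and one reported concentration, so early stoppers are included.

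**The concern.** Section 7.1 sends early stoppers to the SoA, and the SoA has only the Day 1 clock. The text does not say whether such a participant keeps the remaining treatment-period visits without dosing, waits for Week 13, or starts the follow-up block from the last dose. Sites could reasonably do different things.

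Two consequences follow. First, safety is the primary objective, a participant may be stopped for a safety or tolerability concern, and each cohort has about 8 participants. How soon and how often an early stopper is seen after the last dose should not depend on how a site reads Section 7.1. AE collection under Section 8.3.1 runs at least to the final planned follow-up visit, so the anchor also fixes how long AEs are collected.

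Second, trough concentration at Weeks 3 to 15 is the secondary endpoint. A nominal week defines a trough only if the dose before it was given. The SAP does not set that condition, so late washout samples can enter the trough summary under the same label.

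**Working it through.** **Inputs.** Dosing days 1, 22, 43, 64 and 85, follow-up days 92, 99, 106, 127 and 169, and other treatment-period visits on Days 8, 15, 29 and 36 (SoA); follow-up length 12 weeks = 84 days (Section 4.2). All days are nominal, without visit windows.

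**The plan's own figure.** Last planned dose + 84 = 85 + 84 = 169, the Week 24 visit. Sections 1.3 and 4.2 agree exactly for a full course.

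**Early stoppers.** Let L be the day of the last dose. Three readings are available:

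- A: early withdrawal visit, then the follow-up block on its Day 1 dates. First follow-up visit at 92 − L days after the last dose.
- B: the full SoA continues without dosing.
- C: the follow-up block restarts from L, at the intervals a completer has: 92 − 85 = 7, 99 − 85 = 14, 106 − 85 = 21, 127 − 85 = 42, 169 − 85 = 84.

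| Last dose L | A: days to first follow-up visit (92 − L) | A: days to first follow-up clinic visit (106 − L) | A: follow-up visits by L + 84 | B: visits by L + 84 | B: longest gap by L + 84 (days) | C: visits by L + 84 |
|---|---|---|---|---|---|---|
| Day 1 | 91 | 105 | 0 | 8 | 21 | 5 |
| Day 22 | 70 | 84 | 3 | 8 | 21 | 5 |
| Day 43 | 49 | 63 | 4 | 6 | 21 | 5 |
| Day 64 | 28 | 42 | 4 | 5 | 21 | 5 |
| Day 85 (completer) | 7 | 21 | 5 | 5 | 42 | 5 |

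Column A leaves out the early withdrawal visit, whose day is not fixed. If it fell 21 days after the last dose (an assumption), the gap from it to Day 92 would be 92 − (L + 21) = 70, 49, 28 and 7 days for L = 1, 22, 43 and 64.

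**Effect on the Week 15 trough.** The sample is due on Day 106 under both A and B. Time since last dose is 106 − L:

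- L = 1: 105 days
- L = 22: 84 days
- L = 43: 63 days
- L = 64: 42 days
- L = 85: 21 days, the intended interval

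Under B the earlier nominal troughs are affected too. With L = 22, the Week 9 and Week 12 samples are 64 − 22 = 42 and 85 − 22 = 63 days after the last dose.

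**Effect of the anchor on AE collection.** Under A or B the final planned visit is Day 169. Under C it is L + 84 = Day 85, 106, 127 or 148, which is 84, 63, 42 or 21 days earlier.

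**Weight of one participant.** With 8 participants contributing, one early stopper supplies 1/8 = 12.5% of the values in a nominal-week summary.

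**The case against.** A reader might infer that an early stopper has no scheduled follow-up in the weeks after the last dose. The documents do not support that. Section 7.1 requires an early withdrawal visit, and Appendix 19 gives the early termination visit an ECG, vital signs, safety labs, PK, GDF-15 and immunogenicity samples. (Section 7.2 does add that incomplete early termination procedures are not deviations so long as safety was preserved.) Staying on the SoA without dosing is an equally available reading: Section 7.1 says that stopping the drug is not withdrawal from the study, and Section 7.2 says that those who ask to stop treatment continue to be followed. Even under Reading A, only a last dose on Day 1 leaves the 12-week window without a follow-up-block visit.

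Nor do Sections 1.3 and 4.2 contradict each other for the planned course. The Section 4.2 sentence opens by referring to a finished 12-week treatment period, so it need not be a rule for early stoppers.

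Other safeguards exist: unplanned visits (Section 1.3), monthly safety review (Section 8.2), repeat testing of clinically significant laboratory values (Section 8.2.5) and follow-up of each event to resolution or stabilization (Section 8.3.3). Section 7.1 expects permanent discontinuation to be rare.

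All of this stands, and it limits the safety side to an ambiguity. It does not say which reading applies, and it does not reach the trough definition. SAP listings and individual plots do show actual times, but the summaries and the mean and median plots use nominal time. SAP Section 5.3 allows a concentration to be set to missing when a sampling-time deviation is of sufficient concern or the value is flagged anomalous. That is discretionary, and a Day 106 sample is on time by the SoA clock.

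**Conclusion.** The point holds in limited form. Sections 1.3, 4.2 and 7.1 together leave the visit set and the anchor open for participants who stop before Week 12. Depending on the reading, the first follow-up visit comes 28 to 91 days after the last dose, or visits continue with no gap over 21 days in the following 12 weeks. The documents do not settle which is meant.

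The firmer part is in the SAP. Under either reading on the Day 1 clock, the Week 15 trough would include samples 42 to 105 days after the last dose, two to five times the intended 21 days, and nominal-week PK and GDF-15 summaries would mix different times since dosing. If concentrations fall after the last dose, as Section 4.2 anticipates for unbound drug, this pulls the summarized trough down.

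This rests on nominal visit days, on at least one participant stopping early and still giving samples, and on no discretionary exclusion being made. How many will do so cannot be known from the documents. The effect on the treatment-emergent AE window cannot be sized either, because SAP Section 3.1.1 ends it at the last dose plus a lag that it does not quantify.

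**What to change.** **Protocol.** Reconcile Sections 1.3, 4.2 and 7.1 so that one visit set and one anchor are stated for participants who stop PF-06946860 before Week 12. The schedule is the sponsor's to choose. In choosing, the sponsor should note the effect on Section 8.3.1: restarting the block from the last dose would bring the final planned visit, and so the minimum AE collection period, forward by 21 to 84 days.

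**SAP Sections 3.2, 3.3.2, 6.2 and 6.3.2.** Count a sample as a trough only if the preceding scheduled dose was given. Present other PK and GDF-15 samples taken after discontinuation by actual time since last dose, and leave them out of the nominal-week summaries.

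**Cost.** A few lines in each document. The SAP rule needs no new data, because actual sampling times are already recorded. The downside is slightly fewer observations in the nominal-week summaries.

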#### **7.1.1. Criteria for Discontinuation**

Discontinuation of IP must occur for a participant meeting any of the following conditions:

- Criteria for a potential Hy's law case are met (see [Appendix 6](#)).
- Intent to become pregnant or pregnancy confirmed by serum beta human chorionic gonadotropin ( $\beta$ -hCG) testing.

